8.3.10 Collection of Nasal and Nasopharyngeal Swabs and Blood Samples

Refer to [Section 8.5](#) for samples that will be collected for virology assessments. The RSV-specific tests are indicated in [Table 2](#).

8.4 Laboratory and Diagnostic Procedures

At Screening, the rapid viral diagnostic screen will be performed on site. Subsequent virology assessments will be sent to the central laboratory(ies).

On Day 1, enrolled subjects will undergo the clinical laboratory evaluations of blood and urine samples specified [Table 2](#), which will be performed at the local site laboratory (expedited testing and reporting) and the central laboratory(ies). Subsequent clinical laboratory evaluations will be performed by the central laboratory(ies).

The Day 1 collection of blood, urine, and nasopharyngeal swab samples will be completed prior to administration of study drug.

A Laboratory Manual will be provided to the site detailing kit contents, reordering supplies, sample collection, handling, storage, and shipment instructions. All unblinded laboratory values will be reviewed by the Investigator, documented, and the results maintained in the source documents. All out-of-range laboratory findings require an interpretation as to whether or not they are of clinical significance. Clinically significant laboratory findings in the opinion of the Investigator should be recorded as an AE (or SAE as appropriate) (see [Section 9.1](#)).

8.4.1 Routine Laboratory Panels

Blood samples will be collected for analysis of the analytes as shown in [Table 2](#). Samples will be collected from all subjects enrolled into the study.

Blood and urine samples for clinical laboratory assessments will be collected according to the SoA ([Appendix 1](#)) and processed as indicated in the Laboratory Manual. Estimated creatinine clearance will be calculated using the Cockcroft-Gault equation using actual body weight.

8.4.2 Pregnancy and Menopausal Laboratory Testing

All female subjects of childbearing potential will undergo a urine pregnancy test at Screening and at the EOS Visit. In addition, on Day 1, blood will be collected for a serum pregnancy test to be performed by the central laboratory. The screening urine pregnancy test results will be used to qualify subjects at study entry.

To confirm nonsurgical postmenopausal status for women stating that they are amenorrhoeic for 1 to 2 years, documentation of FSH levels >35 mIU/mL will be required. Where such documentation is not available, then FSH levels will be measured on Day 1. In such subjects, urine and serum pregnancy testing should also be performed at Screening, and these subjects will be required to follow appropriate contraceptive practices for women of childbearing potential until a confirming FSH level is available.

Table 2: Clinical and Respiratory Syncytial Virus Laboratory Evaluations

CHEMISTRY PANEL Alanine aminotransferase^a Albumin, serum^a Alkaline phosphatase, serum^a Amylase^a Aspartate aminotransferase^a Bilirubin, total and direct^a BUN^a BUN/Creatinine ratio (calculation) Calcium, serum Creatine kinase Creatinine, serum^a Creatinine clearance, estimated Uric acid Electrolyte panel (sodium, potassium, chloride, bicarbonate)^a Phosphorus Gamma glutamyl transferase Globulin, total Glucose, serum^a Cholesterol Triglycerides Lactate dehydrogenase Lipase Protein, total, serum
	
HEMATOLOGY PANEL Hemoglobin^a Hematocrit^a Differential white blood cell count, percentage and absolute (basophils, eosinophils, lymphocytes, monocytes, neutrophils)^a Mean corpuscular hemoglobin Mean corpuscular hemoglobin concentration Mean corpuscular volume Platelet count^a Red blood cell count White blood cell count^a International normalized ratio^a Prothrombin time^a Activated thromboplastin time^a


URINALYSIS Routine urinalysis to include: Color and appearance, pH, specific gravity, bilirubin, glucose, ketones, leukocytes, nitrite, occult blood, protein, urobilinogen, microscopic examination (including red blood cells and white blood cells)^a
	
RSV-SPECIFIC AND OTHER VIROLOGY TESTS RSV and influenza A/B diagnostic test (nasal or nasopharyngeal secretions) SARS-CoV-2 diagnostic test (nasopharyngeal or oropharyngeal secretions) Confirmatory respiratory pathogen panel RSV RNA quantitation of viral load (nasopharyngeal secretions) [REDACTED] RSV serology (neutralizing antibodies, serum, archived)
 
PREGNANCY AND OTHER TESTS Urine pregnancy test Serum pregnancy test (only Day 1 and to the central laboratory) Follicle-stimulating hormone

Abbreviations: BUN = blood urea nitrogen; RSV = respiratory syncytial virus.

^a On Day 1, blood and urine samples should be taken from all eligible subjects and sent to the local laboratory for these identified tests, which should be assayed and reported in an expedited manner. In parallel, complete hematology, chemistry, and urine panels should be sent to the central laboratory with the other Day 1 samples.

8.5 Virology Assessments

Virology assessments and tests (see [Table 2](#)) will be performed using nasal (or nasopharyngeal) swab (rapid diagnostic screen) or nasopharyngeal swab samples (other virology assessments) and serology samples collected at Screening and at timepoints indicated in the SoA ([Appendix 1](#)) and as further described in the Laboratory Manual, including swab collection, sampling, and handling procedures. Note: Multiple nasopharyngeal swab samples may be collected at each timepoint; refer to the Laboratory Manual for details. With the exception of the rapid diagnostic test (for RSV and influenza A/B) that will be performed at the local site laboratory, all other virology/RSV assessments will be analyzed at the central laboratory(ies).

8.5.1 Respiratory Syncytial Virus, Influenza, and SARS-CoV-2 Rapid Molecular Diagnostic Tests

After a subject reviews and signs the Rapid Viral Screen ICF, the subject will undergo a rapid molecular diagnostic screen for RSV and influenza A/B at the local site. Refer to the Laboratory Manual for details. A nasal (or nasopharyngeal) swab sample will be collected to obtain respiratory secretions. Subjects whose swab sample tests positive for RSV and negative for influenza virus and who agree to proceed, will be required to read and sign the full study ICF and may proceed for further screening assessments. Results will be recorded in the source documents.

In the event that the rapid molecular diagnostic test is unavailable for technical reasons, then rapid antigen tests for RSV and influenza virus may be used as a back-up. The use of such tests and the results must be recorded in the source documents.

Subjects, who sign the full study ICF and whose swab sample test results are positive for RSV and negative for influenza, will be screened for SARS-CoV-2 using a rapid molecular diagnostic test.

8.5.2 Confirmatory Respiratory Pathogen Panel

Following randomization on Day 1, as specified in the SoA ([Appendix 1](#)), eligible subjects will have additional nasopharyngeal swab sample(s) taken prior to taking the first dose of EDP-938 or placebo for central laboratory analysis and confirmation of respiratory pathogens recovered. This testing will be performed to identify other nasopharyngeal co-pathogens that may include adenovirus, coronavirus, human metapneumovirus, human rhinovirus/enterovirus, parainfluenza virus, *Bordetella pertussis*, *Chlamydomphila pneumoniae*, and/or *Mycoplasma pneumoniae*, which may impact the course of a subject's illness. Refer to the Laboratory Manual for further details.

8.5.3 Respiratory Syncytial Virus RNA Quantification of Viral Load

The RSV RNA viral load will be measured in nasopharyngeal swabs by RT-qPCR assay at the timepoints specified in the SoA ([Appendix 1](#)). The RT-qPCR will also be used to determine viral dynamics (eg, peak viral load and time to peak). Refer to the Laboratory Manual for further details.

8.5.4 Respiratory Syncytial Virus Subgroup (A or B) Determination

Nasopharyngeal swab sample(s) will be analyzed to determine whether the virus belongs to RSV subgroup A or B. Refer to the Laboratory Manual for further details.

8.5.5 Viral Resistance

Nasopharyngeal swab sample(s) may be analyzed for potential viral resistance monitoring assessment. Resistance monitoring assessment, if performed, will be conducted by population and/or deep sequencing of the RSV gene to monitor for treatment-emergent resistance mutations. Refer to the Laboratory Manual for further details.

8.5.6 Respiratory Syncytial Virus Serology

At the timepoints specified in the SoA ([Appendix 1](#)), samples will be collected for RSV serology assessment using the RSV neutralization antibody assay. Refer to the Laboratory Manual for further details.

8.6 Pharmacokinetic Samples

Blood (plasma) samples for PK analysis will be collected on Day 1 (postdose; at least 1 hour after dosing or right before the subject leaves the site, whichever is later), Day 3 (at the same approximate time as that of the nasopharyngeal swab collection), and Day 5 (predose).

If the Day 5 study site visit occurs up to 4 hours after the time scheduled for dosing of study drug, then the subject should take the study drug at the site during the visit (refer to the SoA [[Appendix 1](#)]). If the Day 5 study site visit occurs more than 4 hours after the time scheduled for dosing of study drug, then subject should take the study drug at the scheduled time. On Day 5 if the subject takes the study drug prior to the study site visit (see [Section 5.7](#)), a PK sample should be taken at the same approximate time as that of the nasopharyngeal swab collection.

At the EOS Visit, a PK sample is only required for subjects who discontinue the study before the last dose of study drug is taken. The PK sample should be collected at the same approximate time as that of the nasopharyngeal swab collection.

Blood samples will be collected and processed to measure plasma concentrations of EDP-938 [REDACTED] according to the procedures provided and/or approved by Enanta

Pharmaceuticals, Inc. Pharmacokinetic samples will be collected as specified in the SoA (Appendix 1). Additional details will be provided in the Laboratory Manual.

Actual date and time of PK sample collection will be recorded in the eCRF. In addition, the site should record the date and time of last dose taken prior to the PK sample collection. It is important that the date and time of each of PK blood sample are accurately recorded in the source documents.

EDP-938 [REDACTED] in human plasma will be quantified by high-performance liquid chromatography with tandem mass spectrometric detection. The method will be fully validated by assessment of precision, accuracy, sensitivity, and specificity of EDP-938 and its major metabolites by the laboratory selected by Enanta Pharmaceuticals, Inc.

[REDACTED]

[REDACTED]

9. SAFETY MONITORING AND REPORTING

9.1 Definitions

9.1.1 Pretreatment Events

A pretreatment event is any event that meets the criteria for an AE/SAE and occurs after the subject signs the ICF but before receiving the first administration of study drug.

9.1.2 Adverse Events

An AE is any event, side effect, or untoward medical occurrence in a subject enrolled in a clinical study whether or not it is considered to have a causal relationship to the study drug. An AE can therefore be any unfavorable and unintended sign, symptom, laboratory finding outside of normal range with associated clinical symptoms or suspected latent clinical symptoms in the opinion of the Investigator, including those requiring therapeutic intervention, physical examination finding, or disease temporally associated with the use of the study drug, whether or not the event is considered related to the study drug.

The occurrence of AEs should be sought by nondirective questioning of the subject at each study site visit during the study. Adverse events also may be detected when they are volunteered by the subject during or between study site visits or through physical examination, laboratory test, or other assessments.

Planned hospital admissions or surgical procedures for an illness or disease that existed before the subject was enrolled in the study are not to be considered AEs unless the condition deteriorated in an unexpected manner during the study (eg, surgery was performed earlier than planned).

9.1.3 Serious Adverse Events

An SAE is any untoward medical occurrence at any dose that:

- Results in death: This includes deaths that appear to be completely unrelated to study drug (eg, a car accident)
- Is a life-threatening event: An event that places the subject at immediate risk of death at the time of the event; it does not refer to an event that hypothetically might have caused death if it were more severe
- Requires inpatient hospitalization or prolonged hospitalization of an existing hospitalization, unless hospitalization is for:
 - Routine treatment or monitoring of the studied indication, not associated with any deterioration in condition

- Elective or preplanned treatment for a pre-existing condition that is unrelated to the indication under study and has not worsened since signing the ICF
- Treatment on an emergency outpatient basis for an event not fulfilling any of the definitions of a SAE given above and not resulting in hospital admission
- Social reasons and respite care in the absence of any deterioration in the subject's general condition
- Results in permanent or prolonged (at least 28 days in duration) disability or incapacity
- Is a congenital anomaly or birth defect in the offspring of a study subject
- Medically important event: An event that may not be immediately life-threatening, or result in death or hospitalization, or require intervention to prevent one of the outcomes listed above but is considered medically significant for other reasons. An opportunistic or otherwise unusual infection for the Investigator's practice, such as tuberculosis, will be considered medically significant.

The term severe is used to describe the intensity of a specific event (as in mild, moderate, or severe); the event itself, however, may be of minor medical significance (such as severe headache). This is not the same as serious, which is based on outcome of the event, as described above. Seriousness, not intensity, serves as a guide for defining regulatory reporting obligations.

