24. Subjects must not have experienced a severe asthma exacerbation (defined as worsening asthma that requires treatment with oral corticosteroids for 3 or more days, or emergency room attendance) or deterioration in asthma requiring an increase in asthma treatment for at least 6 weeks prior to Screening.
25. Subject is receiving more than two maintenance asthma therapies or theophylline preparations for asthma treatment.
26. Pulse oximetry reading of <90% oxygen saturation measured at rest at Screening.

Additional Exclusion Criteria for Subjects With COPD

27. Receipt of theophylline, roflumilast, maintenance oral corticosteroids, or long-term oxygen therapy (defined as prescribed for 12 or more hours per day).
28. Exacerbation of COPD requiring treatment with systemic corticosteroids and/or antibiotics, or emergency room attendance or hospitalization within 6 weeks prior to Screening.
29. More than three COPD exacerbations with the past 12 months.
30. Pulse oximetry reading of <90% oxygen saturation measured at rest at Screening.

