10. SUBJECT SAFETY MANAGEMENT/ STUDY STOPPING RULES

10.1 Study Stopping Rules

If any of these events occur, dosing will be placed on hold pending a full review of all available clinical safety data and discussion with the investigators and the DSMB.

- Two or more subjects receiving EDP-938 experience a similar Grade 3 study drug-related AE, including a confirmed treatment-emergent Grade 3 laboratory abnormality
- One or more subjects receiving EDP-938 experience a study drug-related SAE
- One or more subjects receiving EDP-938 experience Grade 4 or higher AE or a confirmed treatment-emergent laboratory abnormality regardless of causality attribution to study drug

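### As Protocol 9.1.3 is worded, needing intervention to avert death, admission or disability is not itself a ground for classing an event as serious

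*Protocol*

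**What the plan says.** Protocol section 9.1.3 opens with "An SAE is any untoward medical occurrence at any dose that" and then lists six limbs: death, a life-threatening event, inpatient admission or its prolongation, lasting disability or incapacity, congenital anomaly, and a medically important event.

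The last limb covers an event that need not threaten life, cause death or lead to admission, "or require intervention to prevent one of the outcomes listed above but is considered medically significant for other reasons". One illustration follows: "An opportunistic or otherwise unusual infection for the Investigator's practice, such as tuberculosis, will be considered medically significant".

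The hospitalization limb carries a list of exceptions. One of them is "Treatment on an emergency outpatient basis for an event not fulfilling any of the definitions of a SAE given above", where no admission results.

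Three things depend on SAE status:

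- Protocol 9.2.5 requires the sponsor to be told of an SAE within 24 hours, whatever its presumed relationship to study drug.
- Protocol 10.1 puts dosing on hold if "One or more subjects receiving EDP-938 experience a study drug-related SAE".
- SAP 3.15.1 plans tables of serious TEAEs and of drug-related serious TEAEs.

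**The concern.** The intervention clause is on the side of the sentence that lists what the event need not do. A site that works through 9.1.3 literally finds no criterion that says an event is serious because treatment was needed to stop it becoming fatal, disabling or a cause of admission. The one illustration, an unusual infection, does not point a site towards an acute event that is treated and sent home. The section's closing remark that seriousness rests on the outcome of the event points the other way, because an averted admission leaves no such outcome.

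The study population makes this relevant. The trial treats a respiratory infection and enrols subjects with asthma or COPD, in whom an acute respiratory event managed without admission is plausible. If sites classify such an event differently, its expedited reporting, its place in the serious-event tables and the single-event hold will depend on who reads the sentence.

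**Working it through.** No arithmetic applies. The check has three steps: how the sentence parses, how each limb treats a test case, and what still catches the case if it is not classed as an SAE.

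**1. The sentence.** In "may not be immediately life-threatening, or result in death or hospitalization, or require intervention to prevent one of the outcomes listed above" one *may not* governs three verbs: be, result and require. The qualifying condition comes only after *but*: "but is considered medically significant for other reasons". The natural sense of *may not* is *need not*. On that reading an event that did need intervention is not barred from the limb, but the need for intervention does not admit it either. It must be significant for some other reason.

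**2. Test case.** A drug-related event is treated urgently, admission is averted and the subject goes home.

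- Death: not met.
- Life-threatening: met only if there was immediate risk of death at the time.
- Hospitalization: not met, because it needs an actual admission or prolongation.
- Disability: not met unless it results and is permanent or lasts at least 28 days.
- Congenital anomaly: not applicable.
- Medically important: not met because intervention was needed. Met if the investigator judges the event significant on other grounds.

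No limb makes preventive intervention a ground in its own right. SAP 3.15.1 defines pre-treatment events, TEAEs, relatedness and grades, but not seriousness. Protocol 6.1 points to regulatory SAE definitions, but only for events that prompted unblinding. Urgent intervention also appears in the Grade 4 descriptor in Protocol 9.2.1. That is a severity grade, and 9.1.3 keeps severity apart from seriousness.

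**3. What happens if the event is not classed as an SAE.**

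- 24-hour notification (9.2.5): does not apply.
- Hold trigger for one drug-related SAE (10.1): does not fire.
- Hold trigger for Grade 4 or higher (10.1): fires whatever the SAE status, but only at that grade.
- Hold trigger for Grade 3 (10.1): fires whatever the SAE status, but needs two or more subjects with a similar drug-related event.
- AE recording (9.2.1), the sponsor's ongoing AE review (9.4) and DSMB safety review (9.5): all continue.

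For the hold rule, the uncovered case is therefore one drug-related event, Grade 3 or lower, treated without admission, without immediate risk of death or lasting disability, and not judged significant on other grounds. The 24-hour duty does not depend on relatedness, so for reporting the event need not be drug-related.

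**The case against.** The strongest reply is that the last limb is an open catch-all. *May not* is permissive, the infection sentence only illustrates, and an investigator is free to class an emergency-treated event as significant. Immediate risk of death is caught separately. Two hold triggers do not depend on SAE status, and sponsor and DSMB review continue throughout. Protocol 1.5 reports no SAEs or severe AEs so far, although in healthy subjects and healthy subjects experimentally infected with RSV. The Safety Management Plan cited in 9.2.5 is not available here and may give sites clearer working rules. All of this stands, and it limits the point to wording that leaves classification to discretion the text does not guide.

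A reader might infer more, in four ways that the documents do not support.

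- *That such an event meets no SAE criterion at all.* It can still qualify through the life-threatening limb or the investigator's judgement. Reading *may not* as a prohibition would be needed to exclude it, and that is not the natural sense.
- *That the emergency-outpatient exception cancels the medically important limb.* The exception sits under the hospitalization limb and qualifies only that limb. The limbs are alternatives, so an exception to one does not close another.
- *That exclusion criterion 24 shows the protocol regards these events as serious.* That criterion counts "worsening asthma that requires treatment with oral corticosteroids for 3 or more days, or emergency room attendance" as a severe exacerbation for eligibility. Section 9.1.3 states that severe and serious are different things.
- *That the chance of a missed hold can be stated.* The documents give no rate for emergency-treated events, and a miss would also require drug-relatedness and the failure of every other limb and trigger. Any percentage would rest wholly on assumed rates.

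**Conclusion.** The point holds in a limited form. In Protocol 9.1.3 the need for intervention to avert a listed outcome is not a ground for seriousness. An event of that kind becomes an SAE only through another limb or through a judgement of significance for other reasons.

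The consequence is confined to the uncovered case set out above, but one event is enough to decide the drug-related SAE hold trigger, so the classification of a single case can matter. The event is not lost: it remains in the AE data and in sponsor and DSMB review. What may be lost is its 24-hour notification, its place in the serious-event tables and, if it is drug-related, the automatic hold.

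This rests on the protocol text being what sites apply. If the Safety Management Plan or the SAE form instructions already name preventive intervention as a ground, the practical gap shrinks, but the protocol sentence would then disagree with them. The sentence is an operative definition, so it should be corrected. It does not undermine the safety plan as a whole.

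**What to change.** In the medically important limb of Protocol 9.1.3, place *but* directly after the mention of hospitalization. Follow it with two alternative grounds: that the event requires intervention to prevent one of the listed outcomes, or that it is considered medically significant for other reasons. No new concept needs to be added. Align the SAE form instructions, and check the Safety Management Plan for the same wording.

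A note that the emergency-outpatient exception leaves the other limbs untouched would be a helpful clarification, but it is optional.

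The change moves one clause and updates the matching instructions. It leaves the dosing, the hold thresholds and the analyses as written. The cost is a few more expedited reports, and any additional SAE judged drug-related in a subject on EDP-938 would count towards the existing hold trigger.
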